### *Etiology and risk factors for pancreatitis*

The most common etiologies for pancreatitis include cholelithiasis, alcohol use, and hypertriglyceridemia [[P17-07372](#)]. Other known causes of pancreatitis are trauma, surgery, cancer, anatomical variations of the pancreas and the pancreatic and biliary ducts, hypercalcemia, renal failure, and autoimmune disease [[R20-0778](#)]. Studies have shown that the risk of acute pancreatitis is higher in patients with T2DM and established cardiovascular disease (eCVD) than in patients without these disorders [[R10-6620](#), [R10-2088](#), [R21-0209](#)].

Different studies reported associations between the use of certain diabetes drug classes, for instance incretin-based medications (including dipeptidyl peptidase 4 inhibitors [DPP-4i; such as sitagliptin, saxagliptin, linagliptin, alogliptin] and glucagon-like peptide-1 receptor agonists [GLP-1 RA; such as exenatide, liraglutide, lixisenatide, dulaglutide, semaglutide] [[P13-15588](#)]) and the risk of developing acute pancreatitis.

Potential mechanisms of action for drugs known to cause acute pancreatitis include pancreatic duct constriction (e.g. opioids) or cytotoxic effects that are either direct or due to accumulation of a toxic metabolite or intermediary [[P16-02537](#)].

Pancreatitis reoccurs in up to 25% of patients following hospital admission for their first episode of acute pancreatitis, with smoking and/or alcohol abuse demonstrated as predominant risk factors [[R20-0778](#)].

### *Epidemiology of pancreatitis*

The incidence of acute pancreatitis in T2DM patients varies, with rates from the Clinical Practice Research Databases (CPRD) in the United Kingdom (UK) ranging between 54 and 66 per 100,000 person-years (PY) and rates obtained from insurance claims databases in the United States (US) ranging between 422 and 560 per 100,000 PY [[R10-5391](#), [R10-6620](#), [R10-2088](#)]. The differences between these estimates may be due to the nature of the data sources and the populations studied.

In the past ten years, numerous studies assessed the association between pancreatitis and hypoglycemic agents in the US [[R18-1760](#), [P19-09574](#), [R13-3873](#), [R11-0776](#), [R19-3424](#), [P13-04390](#), [P13-16900](#), [R20-0777](#)], Canada [[P19-09574](#)], UK [[P17-03843](#), [P14-06737](#)], Denmark [[P15-05208](#)], and in Asia [[R19-3425](#), [R19-3426](#), [R19-3427](#), [R19-3428](#), [R19-3429](#), [R11-5180](#), [P16-11950](#), [R19-3430](#)]. Certain diabetes drug classes, for instance incretin-containing medications (including dipeptidyl peptidase 4 inhibitors (DPP-4i; such as sitagliptin, saxagliptin, linagliptin, alogliptin) and glucagon-like peptide-1 receptor agonists (GLP-1 RA; such as exenatide, liraglutide, lixisenatide, dulaglutide, semaglutide) [[P13-15588](#)]), have been associated with the risk of developing acute pancreatitis. Results vary from protective to null associations to 2-3 fold elevated risk of acute pancreatitis depending on the design, population, treatments and comparators studied [[R18-1760](#), [P19-09574](#), [R13-3873](#), [R11-0776](#), [R19-3424](#), [P13-04390](#), [P13-16900](#), [R20-0777](#), [P19-09574](#), [P17-03843](#), [P14-06737](#), [P15-05208](#), [R19-3425](#), [R19-3426](#), [R19-3427](#), [R19-3428](#), [R19-3429](#), [R11-5180](#), [P16-11950](#), [R19-3430](#)]. Recently an observational study was conducted using large claims databases in the US (Truven Marketscan Commercial Claims and Encounters (CCAE) and Medicare Supplemental (MDCR) Database, and Optum Extended Socio-Economic (SES)) to assess the risk of acute pancreatitis in T2DM patients newly exposed to canagliflozin compared to other oral hypoglycemic agents. Six different cohorts of new users of DPP-4is, GLP-1 RAs, sulfonylureas (SUs), thiazolidinediones (TZD), insulin, and other antihyperglycemic agents (AHA) were identified and compared separately with the new users of canagliflozin. Overall, no consistent difference in the risk of acute pancreatitis was observed when comparing canagliflozin with other oral glucose lowering drugs, not with regards to databases, nor with regards to different comparator groups [[RRA-21430](#)]. This inconsistent observation could have several reasons: 1) cohorts were not properly matched concerning previous use of AHA 2) cohorts were not matched with regards to acute pancreatitis risk factors e.g. gall stones 3) concomitant AHA treatment were allowed without restriction. Moreover, because of the heterogenous comparator and residual confounding, no conclusion could be made based on the study results.

Considering methodological challenges discussed above, this voluntarily PASS was designed to investigate the risk of acute pancreatitis in T2DM patients who initiated empagliflozin compared to new users of other oral non-incretin/non-SGLT2i-containing hypoglycemic agents between 1 August 2014 and the latest data-cut available in MarketScan (30 September 2020) and Optum (31 March 2021).

## **8. RESEARCH QUESTION AND OBJECTIVES**

This non-interventional cohort study using data from two large US claims databases will assess the risk of acute pancreatitis among T2DM patients initiating empagliflozin between from 1 August 2014 to the latest data-cut available in MarketScan (30 September 2020) and Optum (31 March 2021).

**Primary Objective:**

To compare the risk of acute pancreatitis in patients with T2DM newly initiating empagliflozin to that of patients newly initiating other oral non-incretin/non-SGLT2i-containing hypoglycemic agents.

## **9. RESEARCH METHODS**

### **9.1 STUDY DESIGN**

This study will use a new user cohort design comparing patients with T2DM who initiated empagliflozin to those who initiated other oral non-incretin/non-SGLT2i-containing glucose lowering drugs, based on electronically recorded longitudinal data from 2 large US claims databases.

### **9.2 SETTING**

Data from 2 large US claims databases (MarketScan and Optum) will be used (from 1 August 2014 to the latest data-cut available in MarketScan (30 September 2020) and Optum (31 March 2021)). The study implements an active comparator new user design and compares patients who newly initiate empagliflozin to those who newly initiate other oral non-incretin/non-SGLT2i-containing glucose lowering drugs. Prior evidence suggested that incretin-based agents may be associated with an elevated risk of pancreatitis, therefore those agents will not be included in the analysis of this study.

#### **9.2.1 Study sites**

See [section 9.4](#). for data sources.

#### **9.2.2 Study population**

All patients with a recorded diagnosis of T2DM who initiated empagliflozin or other oral non-incretin/non-SGLT2i-containing glucose lowering drugs (metformin, SU, or TZD) between 1 August 2014 and 31 October 2020 will be selected from the Truven MarketScan Commercial Claims and Encounters (CCAE), Truven MarketScan Medicare Supplemental (MDCR), and Optum Clininformatics® Data Mart [CDM] databases.

Comparison groups were selected based on clinical guideline recommendations and current real-world patterns of use for oral glucose lowering drugs. First-line therapy in the US and most countries according to the guidelines is metformin. SUs, TZDs, and incretin therapies are the primary non-SGLT2i alternatives for the treatment of T2DM. Several studies have reported associations between use of incretin-based medications (including dipeptidyl peptidase 4 inhibitors [DPP-4i; such as sitagliptin, saxagliptin, linagliptin, alogliptin] and glucagon-like peptide-1 receptor agonists [GLP-1 RA; such as exenatide, liraglutide, lixisenatide, dulaglutide, semaglutide] [\[P13-15588\]](#)) and risk of developing acute pancreatitis. Hence, DPP4is and GLP1RA are excluded from the comparators of this study.

Diabetes is a risk factor for acute pancreatitis [[R10-6620](#), [R10-2088](#)], but there is limited information on the duration and severity of diabetes in the US claims databases. Creating comparison groups based on treatment line might be helpful to decrease residual confounding. Therefore, to assess the risk of acute pancreatitis we decided to conduct head-to-head comparative analyses (pending feasibility assessment and adequate sample size) using the stratified therapy lines outlined below [[P17-01404](#)]:

- Monotherapy: Empagliflozin vs. metformin —> index medication is empagliflozin or metformin
- Dual therapy: Empagliflozin vs. SU (both on a background of metformin) —> index medication is empagliflozin or SU
- Triple therapy: Empagliflozin vs. TZD (both on a background of metformin plus SU) —> index medication is empagliflozin or TZD

Separate analysis of the two databases within each treatment line is the ideal approach. However, if there are not enough study participants in the Optum and MarketScan databases in each therapy line, a meta-analysis of each therapy line will be conducted between Optum and MarketScan (pending heterogeneity and sample size assessments).

Other combinations of empagliflozin (e.g. empagliflozin on a background of SU or TZD, or empagliflozin on a background of SU and TZD) will not be assessed in this study due to the small sample size [Feasibility assessment report November 2021, data on file].

From a feasibility assessment conducted in November 2021, it is known that there are not enough study participants in the Optum and MarketScan database in each therapy line and the dual-therapy cohort was reported with the highest number of empagliflozin initiators. Therefore, a meta-analysis of the dual therapy cohorts including the data from the MarketScan MarketScan and Optum databases will be the main analysis of this study.

Due to low sample size and inadequate power, analysis of the mono- and triple therapy cohorts cannot be assessed.

Overall inclusion and exclusion criteria are listed below:

Inclusion criteria: Patients must meet all of the following criteria to be eligible for inclusion in the study:

- Patients  $\geq 18$  years old
- A diagnosis of T2DM as demonstrated by at least one qualifying diagnosis code (International Classification of Diseases (ICD)-9-CM diagnosis code of 250.x0 or 250.x2; ICD-10-CM diagnosis code of E11.x) from any encounter type recorded in the claims in the 6 months prior to the drug initiation.
- Patients initiating empagliflozin (as monotherapy, on a background of metformin, or on a background of metformin and SU) or qualifying comparator (metformin monotherapy, SU on a background of metformin, or TZD on a background of metformin and SU) during the study period.

- Have at least 6 months of continuous registration in the database prior to initiation of empagliflozin or a comparator drug

Exclusion criteria: Patients meeting any of the following criteria will be excluded from the study:

- Patients with missing or ambiguous age or sex information.
- Use of a SGLT2i, DPP-4i or GLP-1 RA in the 6 months prior to study drug initiation.
- Chronic use of insulin in the outpatient setting in the 6 months prior to the study drug initiation (definition is added to the SEAP). This criterion will help us to remove severe cases of diabetes and reduce the risk of residual confounding as diabetes is a risk factor for developing acute pancreatitis [\[R10-6620, R10-2088\]](#).
- Patients with type 1 diabetes mellitus (T1DM) defined as at least 1 inpatient or outpatient International Classification of Diseases Ninth Revision, Clinical Modification (ICD-9-CM) diagnosis code of 250.x1 or 250.x3 or International Classification of Diseases, Tenth Revision, Clinical Modification (ICD-10-CM) diagnosis code of E10.x in the 6 months prior to the study drug initiation.
- Patients with secondary diabetes or gestational diabetes in the 6 months prior to the study drug initiation.
- Claims for acute or chronic pancreatitis, pancreatic cancer, or other disease of the pancreas any time prior to the study drug initiation.

Treatment line specific inclusion criteria (if feasibility assessment would allow a powered analysis) are:

- For the monotherapy cohort, patients should be new users of empagliflozin or metformin (comparator). To quantify as a new user, no use of either of the two drugs (empagliflozin or metformin) in the previous 6 months is permitted.
- For the dual therapy cohort, patients should be new users of empagliflozin (on a background of metformin) or new users of SU on a background of metformin (comparator). To quantify as a new user, no use of either of the two drugs (empagliflozin or SUs) in the previous 6 months is permitted.
- For the triple therapy cohort, patients should be new users of empagliflozin (on a background of metformin and SU) or new users of TZD on a background of metformin and SU (comparator). To quantify as a new user, no use of either of the 2 drugs (empagliflozin or TZDs) in the previous 6 months is permitted.

All codes used in cohort creation are listed in Appendix 3 and 4.

### **9.2.3      Study visits**

Not applicable.

### **9.2.4      Study discontinuation**

Not applicable.

## **9.3 VARIABLES**

The variables that will be used in this study are described below.

### **9.3.1 Exposures**

For this study, eligible patients will be identified from prescriptions/dispensings for the following study medications of interest (index medications):

Study drug will include:

- New therapy with empagliflozin (index medication) for the treatment of T2DM:
  - As monotherapy
  - As dual therapy (on a background of metformin)
  - As triple therapy (on a background of metformin and SU)

Comparator will be:

- New therapy with an oral non-incretin/non-SGLT2i-containing hypoglycaemic agent for the treatment of T2DM:
  - As monotherapy (metformin monotherapy): index medication is metformin
  - As dual therapy (SU on a background of metformin): index medication is SU
  - As triple therapy (TZD on a background of metformin and SU): index medication is TZD

This leads to the following comparisons:

- Monotherapy: Empagliflozin vs metformin
- Dual therapy: Empagliflozin vs SU, both on background of metformin
- Triple therapy: Empagliflozin vs TZD, both on a background of metformin and SU

Fixed-dose combinations will be considered equivalent to their free combination regimens. For instance, initiators of Synjardy will be categorized as dual therapy of empagliflozin. Combinations beyond triple therapy (i.e., use of 4+ glucose lowering drugs) will not be considered.

The index date is defined as the date of the first recorded claim for a qualifying prescription as a new user. Patients are required to have at least 6 months of continuous registration in the database prior to initiation of empagliflozin or a comparator drug (the look-back period). The look-back period was specified to confirm new medication use (i.e., having a first prescription claim for empagliflozin or other oral non-incretin/non-SGLT2i-containing glucose lowering drugs without use in the prior 6 months) and describe baseline parameters, such as prior medical history and medications. The look-back period includes the index date.

The study will be conducted utilizing a modified “as-treated” approach. Study follow-up will start the day after initiation of index medication and will continue until:

- The first occurrence of the outcome

- The date of end of continuous registration in the database
- The date of death
- The date of study end (31 October 2020)
- The date of discontinuation of index medication (defined as the date of the last date of last dispensing + days supply + grace period). The grace period is a time period after exposure end during which observed outcomes are still attributed to the exposure. Grace period varies according to the specific outcome. In this study, for acute pancreatitis, we have 30 days [[c18659315-02](#)] grace period in the main analysis and 90 days in the sensitivity analysis [[R18-1760](#), [RRA-21430](#), [P20-07536](#)].
- The date of switch of index medication to another hypoglycaemic agent (see [section 9.7.1](#) and SEAP)
- The date of addition of incretin-based therapy (with continuation of index therapy)
- The date of addition of SGLT2i (with continuation of index therapy)
- The date of addition of insulin (with continuation of index therapy)
- The date of addition of the within treatment line comparator index drug (with continuation of index therapy)

All definitions can be found in section 9.7.1. All codes used to define exposure variables are listed in Appendix 4.

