
Name of company:			
Boehringer Ingelheim			
Name of finished medicinal product:			
Jardiance®			
Name of active ingredient:			
A10BK03 Empagliflozin			
Protocol date:	Study number:	Version/Revision:	Version/Revision date:
10/DEC/2021	1245-0201	1.0	NA
	
Cox proportional hazards regression models based on time-to first acute pancreatitis event will be used to estimate hazard ratios (HR) and 95% CIs for each treatment line comparison of interest in the unmatched and PS-matched cohorts. Based on a feasibility assessment conducted in Optum and MarketScan databases using data between 1 August 2014 and the latest data-cut available in MarketScan (30 September 2020) and Optum (31 March 2021), meta-analysis of the dual therapy cohorts including the data from the Marketscan MarketScan and Optum databases will be the main analysis of this study:
 

• Dual therapy: Empagliflozin vs. SU (both on a background of metformin)

 
All results will be presented for each database separately but if there is not enough sample size in each treatment line cohort in each database, after evaluating potential heterogeneity, meta-analysis techniques will be used to pool the treatment line cohorts of the 2 databases. Descriptive tables and all parameter estimates from the main and all sensitivity analyses will be pooled using meta-analytic methods assuming a fixed effects model, to avoid potential biases associated with random effects pooling in the context of few databases [R17-1410].
		
Milestones:	
The study period is between 1 August 2014 (start of data collection) and the latest data-cut available in Marketscan (30 September 2020) and Optum (31 March 2021) (end of data collection). In this multi database study, the start of data analysis will be in December 2021 and the final report will be available in Q3 2022.
		

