## **6. MILESTONES**

Milestone	Planned Date
IRB/IEC approval	Not applicable
Start of data collection	1 August 2014
End of data collection	30 September 2020 for Marketscan and 31 March 2021 for Optum
<Registration in the EU PAS register>	29 November 2021
Start of data analysis	Q4 2021
End of data analysis	Q2 2022
Final report of study results:	Q3 2022

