## **9.5 STUDY SIZE**

All patients with T2DM who newly initiate therapy with empagliflozin or study comparator who meet the inclusion and exclusion criteria will be included in the analysis.

Event rate of acute pancreatitis reported in patients with T2DM who are treated with canagliflozin was reported to be 2.2 per 1000 PY [\[RRA-21430\]](#). This rate was used for sample size calculation using the formula of Farrington and Manning (maximum likelihood method) [\[R14-3295\]](#).

Null hypothesis H0:  $\pi_2 / \pi_1 \geq 1.5$  (non-inferiority)

A single stage (fixed sample size) design was chosen.

For specified  $\alpha = 0.05$  and rates  $\pi_1 = 0.0022$  and  $\pi_2 = 0.0022$  (odds ratio of 1.000) the power (1 -  $\beta$ ) is 80.0% if the test stages consist of the sample sizes given in the last two columns of [Table 1](#).

The computation assumes an allocation ratio (n2/n1) = 1 (Table 1). It is assumed that all patients have 1 year of follow up.

**Table 1** Number of empagliflozin initiators and empagliflozin-exposed person-years needed to detect a HR of 1.5 and 2.0 with a power of 80% and  $\alpha = 0.05$  under 1:1 matching ratio

Hazard ratio (HR)	Information rate	Bunds accept $H_0$	Bunds reject $H_0$	sign.level one-sided	$\alpha$ spent	$\beta$ spent	power achieved	Observations per exposure group	Overall observations
1.5	1.0	1.645	1.645	0.0500	0.0500	-	0.8000	34585.4	69170.8

ADDPLAN Adaptive Design Software 2019 and SAS 9.4 software ( ) were used to calculate the sample size.

Analysis of this study will be initiated as soon as a sufficient sample size to exclude a HR of 1.5 with 80% power is reached. Based on a feasibility assessment conducted in Optum and MarketScan databases using data between 1 August 2014 and the latest data-cut available in MarketScan (30 September 2020) and Optum (31 March 2021), the dual-therapy cohort was reported with the highest number of empagliflozin initiators, therefore meta-analysis of the dual therapy cohorts including the data from the MarketScan and Optum databases will be the main analysis of this study as it will be the only powered analysis.

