6.2.1 Study period

The patient selection period will be from 01 August 2014 to the latest data-cut available in Marketscan (30 September 2020) and Optum (31 March 2021). Patients will be selected into the study at any time during this period once they fulfil the study eligibility criteria.

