7.1 EXPOSURES

Please check section 9.3.1 of the study protocol.

7.1.1 Operational definitions on how to identify each of the index medication cohorts:

For index medication determination, we first select all patients with any of Empagliflozin, TZD, SU and Metformin prescriptions within study period. Then we evaluate index drug for each patient following this order: Empagliflozin → TZD → SU → Metformin. Therefore, each patient will be classified into one of index cohorts only once. The details for Empagliflozin initiators are provided below and all other drugs follow the same approach.

Empagliflozin initiators:

1. Between Aug 2014 and latest data cut we will choose all Empagliflozin new users. The date of first Empagliflozin prescription will be selected as index date. New users should not have any prescriptions for Empagliflozin in 6 months prior to the index date.
2. In the next step we will check which of the Empagliflozin initiators use metformin, or SU in the 6-month baseline period

[figure not shown]

Figure 1

Diagram for Mono, Combo or Triple groups creations

Code list for exposure variables is available in [Annex 2](#).

The index date in both groups will be the date of prescription of empagliflozin or other hypoglycaemic therapies (index medication), and the planned study follow-up period starts at the day after index date.

Proprietary confidential information © 2022 Boehringer Ingelheim International GmbH or one or more of its affiliated companies

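### The 31 October 2020 study end in Protocol 9.2.2 and 9.3.1 matches neither database's data cut and, taken literally, drops the last five months of Optum

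*Protocol*

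**What the plan says.** Two sections of the protocol use a single calendar date for both databases. Section 9.2.2 states that initiators "between 1 August 2014 and 31 October 2020 will be selected" from the MarketScan and Optum sources together. The censoring list in 9.3.1 includes "The date of study end (31 October 2020)".

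The other dated statements of the window are database-specific:

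- Abstract, Milestones entry: "The study period is between 1 August 2014 (start of data collection) and the latest data-cut available in Marketscan (30 September 2020)", followed by 31 March 2021 for Optum.
- Section 6, end of data collection: "30 September 2020 for Marketscan and 31 March 2021 for Optum".
- Section 9.5: the feasibility assessment was run "using data between 1 August 2014 and the latest data-cut available in MarketScan (30 September 2020) and Optum (31 March 2021)".
- SAP 6.2.1: patient selection runs to the "latest data-cut available in Marketscan (30 September 2020) and Optum (31 March 2021)".

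Section 9.2 and SAP section 5 give the same pair of dates. SAP 7.1.1 is consistent with them: "Between Aug 2014 and latest data cut we will choose all Empagliflozin new users".

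The remaining censoring lists name a study end without dating it: the abstract's Data analysis entry, Table 2 in 9.7.1, section 9.7.3, item 3 of 9.7.6, and the text of SAP 7.1.3. For exposures, SAP 7.1 says: "Please check section 9.3.1 of the study protocol". Neither document records an amendment, so both October entries are current text.

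**The concern.** The study end date is an operative rule. It fixes which initiators enter and how much person-time and how many events reach the primary analysis. Section 9.5 makes the pooled dual-therapy comparison the main analysis because it is the only powered one, and the feasibility work behind that choice used the later cuts. If a programmer applies the one dated censoring rule, the analysis will hold less Optum data than that assessment covered.

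The two documents can also be combined badly. If entry follows the SAP (to 31 March 2021 in Optum) and follow-up ends as in 9.3.1, every Optum initiator indexed from 31 October 2020 onward is eligible but contributes no time, because follow-up starts the day after the index date. Under 9.2.2 and 9.3.1 together, this affects only someone indexed on 31 October 2020 itself.

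Section 9.8 has two analysts work independently and requires their results to agree. With two end dates in the text, each could choose a different one in good faith.

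**Working it through.** **Plan's own figure.** The Farrington-Manning ratio formula with constrained maximum-likelihood estimates, p1 = p2 = 0.0022, null ratio 1.5, one-sided alpha 0.05, power 80% and 1:1 allocation gives 34,585.41 per group. Protocol 9.5 states 34,585.4. The requirement does not depend on calendar dates, so the conflict affects only the data available to meet it.

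**Calendar days, both end dates counted, from 1 August 2014.**

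| End date | Source | Days |
|---|---|---|
| 30 September 2020 | MarketScan cut | 2,253 |
| 31 October 2020 | 9.2.2 and 9.3.1 | 2,284 |
| 31 March 2021 | Optum cut | 2,435 |

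- MarketScan: 2,284 − 2,253 = 31 days beyond the data, so nothing is lost.
- Optum: 2,435 − 2,284 = 151 days lost; 151 / 2,435 = 6.2%.

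**Secondary analyses, Optum only.**

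- Intention-to-treat analysis (9.7.6 item 3), taking 12 months as 365 days after the index date: the last index date with complete follow-up is 31 March 2021 − 365 days = 31 March 2020 under the data cut, and 31 October 2020 − 365 days = 1 November 2019 under 9.3.1. Later initiators are not excluded; their follow-up is truncated.
- Optional COVID-19 look (9.9.4), if it uses outcomes within follow-up: from 1 April 2020 there are 365 days to the Optum cut and 214 days to 31 October 2020; 151 / 365 = 41.4% less.

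**Power, as an illustration only.** The documents give no counts by database or calendar time. Assumptions: the cohort is exactly at the required size, Optum contributes 25%, 50% or 75% of events, and Optum events accrue either evenly or in linearly rising fashion over the window.

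- Expected events: E = 2 × 34,585.4 × 0.0022 = 152.2.
- Power = Φ(ln 1.5 × √E / 2 − 1.645) = 80.4%. This is an event-based approximation, which is why it differs slightly from the plan's 80.0%.
- Share of Optum events lost: 6.2% (even), or 1 − (2,284 / 2,435)² = 12.0% (linear).
- Remaining events = 152.2 × (1 − share × loss).

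| Optum share | Even accrual: events, power | Linear accrual: events, power |
|---|---|---|
| 25% | 149.8, 79.9% | 147.6, 79.3% |
| 50% | 147.5, 79.3% | 143.0, 78.2% |
| 75% | 145.1, 78.7% | 138.5, 77.1% |

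The surplus over the required size that would offset the loss is 1 / (1 − share × loss) − 1, which runs from 1.6% to 9.9%.

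**The case against.** The strongest reply is that the sponsor's intention is clear. The data cuts appear throughout both documents, the abstract defines the study period by them, and SAP 7.1.3 lists database versions of Optum Q1 2021 and CCAE Q3 2020 in its censoring material. Section 9.3.1 itself refers to 9.7.1 for definitions, and SAP 6.2.3 sends the end of follow-up to protocol Tables 2 and 3. The figure in SAP 7.1.3 is not available and may show the dates. Independent double programming should expose any divergence before reporting.

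Much of this stands. The October date is probably a leftover, and cohort entry is settled by the SAP. For the end of follow-up, however, the cross-references lead to undated entries, so 9.3.1 remains the only censoring list seen to print a date. The database versions support the data cuts only by inference. Double programming would catch two different choices, but not two analysts who both apply 9.3.1 as written.

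It is also fair to say that the power range rests entirely on assumptions and that the COVID-19 analysis is optional. Only the day counts follow directly from the documents.

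**Conclusion.** The contradiction is real, is in current text, and should be corrected. Followed literally, 9.3.1 discards 151 of 2,435 Optum days (6.2% of calendar time, not person-time) and leaves MarketScan unchanged. The loss in person-time and events cannot be derived from the documents. Under the stated assumptions power falls from 80.4% to between 77.1% and 79.9%, and a cohort about 2% to 10% above the required size would absorb that. The consequence is a modest loss of precision and an avoidable ambiguity in the primary analysis; nothing here implies bias in either direction.

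**What to change.** In Protocol 9.2.2 and 9.3.1, replace 31 October 2020 with 30 September 2020 for MarketScan and 31 March 2021 for Optum. Give the same study end dates in Table 2, 9.7.3, 9.7.6 item 3 and SAP 7.1.3, either in full or by reference to one dated definition. Section 9.8 requires the protocol change to be documented as an amendment; update the SAP to match.

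The cost is two corrected dates and three added date lines in the protocol, one added line in the SAP, and one amendment. No new data are needed and the sample size calculation does not change.
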